7.3. AESI Definition and Conventions

The AESI consist of a list of preferred terms grouped by specific category (for example, pulmonary events, gastrointestinal events categories) and/or by subcategory (for example, diabetes). These categories and subcategories are defined based on MedDRA, and the list that is most current at the time of analysis will be used. Also, changes may be made to this list with each new version of MedDRA.

7.4. Time-to-Onset Definition

Time-to-onset of AESI (any grade) for a specific category (for example, pulmonary events, gastrointestinal events) is defined as the time between the day of the first dose of study drug and the onset date of the earliest AESI (of any grade) in this category.

If the patient did not experience an AESI (of any grade) in the category, time-to-onset will be censored at the maximum follow-up time of that patient (that is, for patients without an event,

time-to-onset will be censored at last dosing date +30 days if patients are off treatment and followed for at least 30 days, otherwise it will be censored at the last known alive date.). If patients experience AESI for a specific category but with event start date after the last dosing date +30 days, time-to-onset will be censored at last dosing date +30 days. The resulting Kaplan–Meier plot will represent the cumulative rate of the AESI (any grade) in the category over time.

Time-to-onset of AESI (Grade 3-5) for a specific category is defined similarly but restricted to Grade 3-5 AESI.

Time-to-onset of drug-related (Grade 3-5 or any grade) AESI for a specific category is defined similarly but restricted to drug-related AESIs.

Time-to-onset for a specific subcategory is defined similarly but restricted to events in this subcategory.

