5.6. Safety Analyses

All safety analyses will be performed for each cohort using the All Treated Population, unless otherwise specified.

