5.6.2.6. Adverse Events of Special Interest

Incidence

Adverse events of special interest (AESIs) will be summarized:

- Summary of AESIs with the number and percentage of patients reporting AESIs, serious AESIs, grade ≥ 3 AESIs, AESIs leading to study drug discontinuation, interruption and dose reduction, and AESIs with the outcome of death.
- Summary of AESIs by worst CTC grade (grade 1, 2, 3, 4, 5, any grade, Grade ≥ 3) presented by category or subcategory / PT

A by-patient listing of AESI will also be provided.

Time to Onset

Time-to-onset of selected AESI (eg, hyperphosphatemia) will be graphically displayed using the Kaplan-Meier technique.

- Time-to-onset of any grade AESI
- Time-to-onset of Grade ≥ 3 AESI

The derivation of time-to-onset of AESI is detailed in Section 7.4.

Time to Resolution

Time-to-resolution of selected AESI (eg, hyperphosphatemia) will be summarized.

- Time-to-resolution of Grade ≥ 3 AESI

The following summary statistics will be reported: percentage of subjects who experienced the specific events, percentage of subjects with resolution of the AESI (clustered), median, 1st quartile and 2nd quartile of time-to-resolution along with 95% CI (derived from Kaplan-Meier estimation) and ranges.

Time-to-resolution of Grade ≥ 3 AESI (eg, hyperphosphatemia) will be graphically displayed using the Kaplan-Meier technique.

Time-to-resolution analyses are restricted to patients who experienced the specific events. Collapsing selected AE and derivation of time-to-resolution of AESI is detailed in Section 7.5.

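### The Kaplan–Meier time-to-onset plot for AESIs is labelled a cumulative rate, which it overstates for later-onset events

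*SAP*

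**What the plan says.** SAP 5.6.2.6 plans the output: "Time-to-onset of selected AESI (eg, hyperphosphatemia) will be graphically displayed using the Kaplan-Meier technique", for any grade and for Grade 3 or higher. SAP 7.4 supplies the definition. Time runs from first dose to "the onset date of the earliest AESI (of any grade) in this category". For a patient without an AESI, "time-to-onset will be censored at last dosing date +30 days if patients are off treatment and followed for at least 30 days", and "otherwise it will be censored at the last known alive date". An AESI that starts more than 30 days after the last dose does not count, and that patient is also censored at last dose plus 30 days. The section then says that the Kaplan–Meier "plot will represent the cumulative rate of the AESI (any grade) in the category over time".

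The rule does not mention death, and the SAP plans no competing-risk estimator.

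AESI frequency is also tabulated. SAP 5.6.2.6 lists a "Summary of AESIs with the number and percentage of patients reporting AESIs". SAP 5.6 sets the denominator: "All safety analyses will be performed for each cohort using the All Treated Population, unless otherwise specified". SAP 7.2 restricts AE summary tables to on-treatment events, and SAP 5.6.2.7 adds exposure-adjusted AESI rates.

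**The concern.** A patient who dies on treatment, or within 30 days of the last dose, without a prior AESI cannot meet the first censoring condition, because follow-up did not last 30 days after the last dose. That patient falls under the residual clause and is censored at the last known alive date. Kaplan–Meier then treats the patient as still able to have the AESI later, in the same proportion as those who remain. Patients who stop drug are handled the same way 30 days after the last dose.

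So 1−KM estimates the probability of an AESI in a population in which nobody dies and treatment never ends. That is a definable quantity, but it is not the proportion of treated patients who will have had the event by a given time, which is how a reader will take a cumulative rate. The bias has one direction: the curve is too high whenever AESI-free exits precede later onsets. Safety and tolerability is a secondary objective in every cohort, and SAP 7.3 illustrates AESI categories with pulmonary events, gastrointestinal events and diabetes, so the curves need not be confined to early events.

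**Working it through.** The documents give no AESI rate, onset time or on-treatment death rate, so there is no planned figure to reproduce. Every rate below is an assumption.

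**Inputs (constant monthly hazards).** AESI h = 0.02 or 0.05; death in the window d = 0.01 to 0.03; discontinuation w = 0.08 to 0.12; t = 12 months.

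**Formulas.**
- Curve as planned: 1−KM = 1 − exp(−ht).
- Cumulative incidence with competing hazard c: CIF = h/(h+c) × [1 − exp(−(h+c)t)], with c = d for death alone and c = d + w when discontinuation also ends the window.

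**Step 1: death alone.**

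| h | d | 1−KM | CIF, death competing | Overstatement |
|---|---|---|---|---|
| 0.02 | 0.01 | 1 − exp(−0.24) = 21.3% | 0.667 × (1 − exp(−0.36)) = 20.2% | 1.2 points |
| 0.02 | 0.03 | 21.3% | 0.400 × (1 − exp(−0.60)) = 18.0% | 3.3 points |
| 0.05 | 0.01 | 1 − exp(−0.60) = 45.1% | 0.833 × (1 − exp(−0.72)) = 42.8% | 2.3 points |
| 0.05 | 0.03 | 45.1% | 0.625 × (1 − exp(−0.96)) = 38.6% | 6.5 points |

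At 6 months the same inputs give an overstatement of only 0.3 to 2.1 points.

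**Step 2: discontinuation also ends the window.**

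| h | d + w | On-treatment share | 1−KM ÷ share | Share with d = 0 |
|---|---|---|---|---|
| 0.02 | 0.01 + 0.08 | 0.182 × (1 − exp(−1.32)) = 13.3% | 1.60 | 0.200 × (1 − exp(−1.20)) = 14.0% |
| 0.02 | 0.03 + 0.12 | 0.118 × (1 − exp(−2.04)) = 10.2% | 2.08 | 0.143 × (1 − exp(−1.68)) = 11.6% |
| 0.05 | 0.01 + 0.08 | 0.357 × (1 − exp(−1.68)) = 29.1% | 1.55 | 0.385 × (1 − exp(−1.56)) = 30.4% |
| 0.05 | 0.03 + 0.12 | 0.250 × (1 − exp(−2.40)) = 22.7% | 1.98 | 0.294 × (1 − exp(−2.04)) = 25.6% |

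The last column isolates the cause. In the first row the gap between curve and share is 21.3 − 13.3 = 8.0 points, and 21.3 − 14.0 = 7.3 of those remain when nobody dies. In the last row the figures are 45.1 − 22.7 = 22.4 points and 45.1 − 25.6 = 19.5.

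**Step 3: simulation of the SAP 7.4 rule.** Each scenario used 400,000 patients, follow-up of 6 to 30 months and a median time on treatment of 3 or 6 months. The AESI reached 30% at 12 months (constant or late-rising hazard) or was early (90% of patients susceptible, mean onset 0.3 months).

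- *Death effect, 30% AESI, month 12.* 1−KM exceeds the Aalen–Johansen estimate with death competing by about 1–2 points when 5% of patients die in the window, 2–4 points at 10% and 4–9 points at 20%.
- *Death effect, early AESI.* 90.0% against 88.8–89.9%, so about 1 point or less.
- *Curve against table, no deaths.* 1−KM is about 30%. The table shows 13.5% (median treatment 3 months) or 20.1% (6 months) for a constant hazard, and 8.4% or 17.7% for a late-rising one.
- *Both death and treatment stop competing, no deaths, month 12.* 13.3% and 18.7% (constant), 8.0% and 14.5% (late-rising). These lie close to the tables, which also count onsets after month 12.

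**The case against.** The strongest case on the other side has four parts.

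1. **It is a legitimate quantity.** The censoring rule is written out, so a careful reader can see that the curve describes onset while treatment (plus 30 days) continues. Kaplan–Meier with that censoring estimates something meaningful, and preferring Aalen–Johansen is partly a choice of target. This stands, but the target the SAP names is the cumulative rate, and the estimator does not deliver it.
2. **Little depends on it.** The time-to-onset output is a graph with no test or decision rule. Crude and exposure-adjusted AESI tables are reported alongside. This stands and keeps the point minor.
3. **The only AESI named for the plot is hyperphosphatemia.** Protocol Table 8 has phosphorus tested 4 days after Cycle 1 Day 1, which suggests that early onset is anticipated; an early event is hardly affected. This stands for that event, although the documents give no onset time and do not say which other AESIs will be plotted.
4. **Precision is poor in the small cohorts.** With the assumed hazards, exp(−2.40) = 9% to exp(−1.32) = 27% of patients are still at risk at 12 months: about 3–9 of 35 in Cohort B and 2–5 of 20 in Cohort C. A bias of 1–7 points is well inside sampling error there. This also stands, though it does not justify the label.

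A reader might also infer that censoring deaths is why the curve and the n (%) tables will disagree. The working does not support that: most of the gap remains with no deaths, because it comes from censoring at last dose plus 30 days and at data cut-off. Nor does the survival follow-up target of 75% deaths show that many AESI onsets are censored by death. It concerns overall mortality, and deaths after the 30-day window play no part in this plot.

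**Conclusion.** The point holds as a minor correction. Under SAP 7.4, AESI-free deaths in the window are censored by implication and treatment stop is censored explicitly, so 1−KM is not the cumulative rate that the SAP says the plot represents. It overstates the actual cumulative probability of later-onset AESIs.

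On the assumed hazards, at 12 months 1−KM reads 21% or 45%, against 18–20% or 39–43% with death competing: about 1 to 7 points too high. For early-onset AESIs the difference is about 1 point or less. The disagreement with the on-treatment tables is a separate and larger matter. With discontinuation included, the share is 10–29% and the curve reads 1.55–2.1 times as high, mainly because of censoring at treatment stop and, in real data, at data cut-off.

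The direction follows from the rule itself. The sizes depend on assumed rates that the documents do not give, so no particular overstatement can be asserted for this trial.

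**What to change.** In SAP 5.6.2.6 and 7.4:

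- State explicitly how AESI-free death in the window is handled.
- Plot the Aalen–Johansen cumulative incidence with AESI-free death in the window as a competing event.
- If the target is on-treatment incidence comparable with the n (%) tables, also make the end of the on-treatment window (treatment stop plus 30 days) a competing event. Treating death alone as competing corrects the death bias but will not bring the curve into line with the tables.
- If a Kaplan–Meier plot is kept, do not call it the cumulative rate. Label it as onset while treatment (plus 30 days) continues.

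The cost is SAP wording and a standard procedure option; no new data are needed. The one small downside is that the curves will not be directly comparable with Kaplan–Meier plots in earlier reports.

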7.5. Time-to-Resolution Definition

In order to derive the time-to-resolution, overlapping or contiguous AESIs within a specific category will be collapsed into what will be termed “clustered” AESIs. For example, if a patient (without pre-treatment AE) experienced an AE from 01 January to 05 January, another AE (with different PT but within same category) from 06 January to 11 January, and the same AE from 10 January to 12 January, these will be collapsed into one clustered AESI from 01 January (onset date) to 12 January (resolution date). [Table 20](#) summarizes key derivation steps for each type of clustered select AEs.

Time-to-resolution of AESI (any grade) for a specific category is defined as the longest time from onset to complete resolution or improvement to the grade at baseline among all AESI clusters in this category experienced by patients. Events which worsened into Grade 5 events (death) or have a resolution date equal to the date of death are considered unresolved. If a clustered AESI is considered to unresolved, the resolution date will be censored to the last known date that the patient was alive. Improvement to the grade at baseline implies that all different AE events in the clustered AESI should at least have improved to the corresponding (that is, with same preferred term) baseline grade (or improve to a lower grade). Time-to-resolution is defined only for patients who experienced at least one AESI in the specific category.

The time-to-resolution of AESI (Grade 3-5) for a specific category is defined similarly, with an onset date corresponding to a Grade 3-5 AESI.

Time-to-resolution of drug-related AESI (any grade or Grade 3-5) is defined similarly but restricted to drug-related AESIs.

Time-to-resolution for a specific subcategory is defined similarly but restricted to events of this subcategory.

Table 20: Derivation of Clustered AESIs

Type of clustered select AE	Derivation
Any grade	Collapse any on-treatment AESI from the same category

Type of clustered select AE	Derivation
Drug-related of any grade	Collapse any on-treatment drug-related AESI from the same category
Grade 3-5	Collapse any on-treatment AESI from the same category. Resolution will be based on the onset date of the earliest Grade 3-5 records (clusters with only Grade 1-2 should not be selected)
Drug-related of Grade 3-5	Collapse any on-treatment drug-related AESI from the same category. Resolution will be based on the onset date of the earliest Grade 3-5 record (clusters with only Grade 1-2 should not be selected)

Abbreviations: AE=adverse event; AESI=adverse event of special interest.

The algorithm for collapsing selected AE records is using the following conventions. For each patient and specified category, the corresponding AE records will be collapsed when:

- Multiple AE records have the same onset date.
- The onset date of an event record is either the same day or 1 day later than the resolution date of a preceding event record (contiguous events).
- The onset date of an event record is after the onset date and prior to or on the resolution date of a preceding event record (overlapping events).

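### SAP 7.5 takes each patient's longest AESI cluster without giving unresolved clusters precedence, so a shorter fatal or ongoing last cluster can be replaced by an earlier resolved one

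*SAP*

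**What the plan says.** SAP 7.5 first merges AESI records of one category into clusters. Records merge only if they share an onset date, follow on within a day, or overlap ("The onset date of an event record is after the onset date and prior to or on the resolution date of a preceding event record"). Episodes separated by a gap stay separate.

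Time-to-resolution for the category then "is defined as the longest time from onset to complete resolution or improvement to the grade at baseline among all AESI clusters". Two rules deal with episodes that do not resolve: "Events which worsened into Grade 5 events (death) or have a resolution date equal to the date of death are considered unresolved", and "If a clustered AESI is considered to unresolved, the resolution date will be censored to the last known date that the patient was alive". No sentence says which cluster represents a patient who has both a resolved and an unresolved one.

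The version planned for output follows the same rule: "The time-to-resolution of AESI (Grade 3-5) for a specific category is defined similarly, with an onset date corresponding to a Grade 3-5 AESI". SAP Table 20 adds that all grades in the category are collapsed first, that the clock starts at the earliest Grade 3-5 record, and that clusters with only Grade 1-2 records are not selected.

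Under Time to Resolution, SAP 5.6.2.6 reports for Grade 3 or higher AESIs the "percentage of subjects with resolution of the AESI (clustered") together with Kaplan-Meier summary statistics and a plot. Hyperphosphatemia is the named example.

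**The concern.** Taking the longest episode looks cautious, and for duration it is. For status it is not, because completed lengths and truncated lengths are ranked together as if they measured the same thing. A fatal episode, or one that began just before last contact, has a short recorded length because observation stopped, and so it tends to lose the comparison. The provision that fatal episodes are unresolved then has no effect for that patient.

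Several clusters per patient are foreseeable. SAP 5.6.2.7 plans to tabulate patients with 2-3 and with 4 or more unique AESI instances, and the hyperphosphatemia guidance in protocol Table 8 provides for repeated interruption and resumption of study drug.

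At stake is the descriptive statement of how often Grade 3 or higher AESIs reverse. If the rule changes the percentage resolved at all, it raises it.

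**Working it through.** The plan states no figure for this point, so there is none to reproduce. The check applies the SAP 7.5 algorithm to constructed patients.

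**Check of the coding.** The SAP's own example (records 01-05, 06-11 and 10-12 January) collapses to one cluster, 01 to 12 January, as the SAP says.

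**Which cluster is unresolved.** An ongoing record has no end date, so every later record overlaps it and merges. Nothing follows a fatal cluster. The unresolved cluster is therefore always the patient's last, and any cluster that displaces it is earlier.

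**Constructed patients (assumed dates).**

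| Earlier cluster | Last cluster | SAP rule | Unresolved-first rule |
|---|---|---|---|
| resolved, 30 days | fatal at 10 days | 30, resolved | 10, censored |
| resolved, 30 days | ongoing, last contact at 14 days | 30, resolved | 14, censored |
| resolved, 30 days | ongoing, last contact at 184 days | 184, censored | 184, censored |
| resolved, 7 days | fatal at 10 days | 10, censored | 10, censored |

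The status is wrong only when the unresolved cluster is the shorter.

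**Chance that the unresolved cluster is hidden.** Assume that the resolved length R is exponential with mean m1 and the censored length C is exponential with mean m2. Then P(R > C) = m1/(m1 + m2).

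| m1 (days) | m2 = 7 | m2 = 30 | m2 = 180 |
|---|---|---|---|
| 7 | 50.0% | 18.9% | 3.7% |
| 14 | 66.7% | 31.8% | 7.2% |
| 28 | 80.0% | 48.3% | 13.5% |

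If C is instead uniform on (0, T), P(R > C) = (m1/T)(1 − exp(−T/m1)). For m1 from 10 to 30 days this is 0.32 to 0.63 at T = 30, and 0.06 to 0.17 at T = 180. The result depends mostly on how long unresolved episodes are followed.

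**Effect on the outputs (20 assumed patients).** Let the longest cluster be resolved in all 20, with durations 5, 7, 7, 8, 9, 10, 10, 12, 14, 14, 15, 16, 18, 20, 21, 22, 25, 28, 30 and 30 days. If 1, 2 or 4 of them also have a shorter unresolved last cluster, the SAP rule reports 20/20 = 100% resolved. The unresolved-first rule reports 19/20 = 95%, 18/20 = 90% or 16/20 = 80%.

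**Effect on the Kaplan-Meier median.** Under the SAP rule, 10 of 20 have resolved by day 14, so the median is 14. Now let the four patients with the longest durations be represented by a fatal cluster censored at day 4. That leaves 16 at risk, of whom 8 have resolved by day 12, so the median is 12. Correcting the status but censoring deaths in the ordinary way makes resolution look faster. If the four deaths are competing events, the denominator stays at 20. The cumulative proportion resolved is then 8/20 = 40% at day 12, 10/20 = 50% at day 14, and at most 16/20 = 80%.

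**The case against.** The strongest reply is that the situation is rare in the output actually planned. Because Table 20 collapses all grades first, low-grade records join neighbouring Grade 3 episodes into one cluster. A patient is affected only with two clusters separated by a gap in every record of the category, each containing a Grade 3-5 record, the last one unresolved and shorter. Cohorts are planned at 20 to 100 patients, and only those with the event enter. This stands and limits the size.

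A second reply is that censoring runs to last known alive. Survival contact is planned every 12 weeks (protocol 3.3.5), and SAP 4.3 sets the final analysis after at least 6 months of follow-up or study discontinuation. Many ongoing, non-fatal episodes will therefore carry censored times of months and win the comparison. This also stands. The problem is concentrated in fatal episodes and in episodes starting shortly before last contact.

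A third reply is that the text can be read differently. A cluster that never resolves could be held to have the longest time and be kept as censored. The SAP does not say so. It gives an unresolved cluster a censoring date, hence a finite length to be compared. On a stricter literal reading, an unresolved cluster has no time to resolution and drops out whenever another resolved. Text that permits three derivations needs settling.

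A reader might also infer that the SAP expressly reports such patients as resolved. It does not: 5.6.2.6 never says how the percentage is derived, and using the selected cluster is the natural reading only. Nor are fatal cases lost from the report. The AESI incidence summary in 5.6.2.6 covers "AESIs leading to study drug discontinuation, interruption and dose reduction, and AESIs with the outcome of death", and AESIs are listed by patient.

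**Conclusion.** The point holds as a gap in the rule. On the text as written, a shorter unresolved last cluster is replaced by an earlier resolved one, and I found nothing in the SAP or protocol that overrides this. It is minor. It affects one descriptive safety summary, the percentage resolved and the Kaplan-Meier time-to-resolution for Grade 3 or higher AESIs, and no efficacy endpoint.

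Its size cannot be fixed from the documents, which give neither recurrence rates nor episode lengths. Under the exponential assumptions, the chance of hiding an unresolved cluster is about 4% to 80%. A reader might go on to infer a definite understatement of the unresolved share. With a hiding chance near 0.5, and 30% to 50% of unresolved patients having an earlier resolved cluster, it would be 0.3 × 0.5 = 15% to 0.5 × 0.5 = 25% in relative terms. The documents support neither input. Over the full range of hiding chances, the same 30% to 50% gives 0.3 × 0.037 = 1% to 0.5 × 0.80 = 40%. No single figure should be quoted.

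**What to change.** In SAP 7.5, define status before time. A patient with any unresolved cluster in the category (for the Grade 3 or higher output, any unresolved cluster containing a Grade 3-5 record) is unresolved and is represented by the longest unresolved cluster. Only a patient whose qualifying clusters all resolved counts as resolved, with the longest resolved time as the event. State in 5.6.2.6 that the percentage with resolution uses this status.

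That change alone leaves the shortened Kaplan-Meier median shown above. Either treat death with an unresolved AESI as a competing event, or report the percentage unresolved beside the curve, with fatal and ongoing cases shown separately.

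The cost is a few sentences and a small programming change, with no new data. The percentage resolved may come out slightly less favourable.

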3.3. Study Periods and Visits for Each Patient

The study periods / visits described in this section are defined for all patients. Please see the schedule of events for an outline of all assessments to be performed during each study period / visit.

For all patients, the Safety Assessment Period begins at the time informed consent has been documented and continues until at least 30 days after the last dose of futibatinib. After the 30-day Safety Follow-Up Visit (see below), patients who have not started treatment with a new anticancer therapy will be assessed for drug-related serious adverse events (SAEs) only.

For each patient, the Study Duration is defined as the time informed consent has been documented to the last day of Disease Assessment Follow-up / Survival Follow-up (see below).

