3.3.3. Safety Follow-Up Period and 30-Day Safety Follow-Up Visit

The Safety Follow-Up Period is the time from the date of last dose of study drug through the 30-Day Safety Follow-Up Visit, which must be performed 30 days (+7 days) following the last dose of study drug. If the patient starts new anticancer therapy within 30 days of the last dose of study drug, the 30-Day Safety Follow-Up Visit should be performed before the start of new anticancer therapy. Every effort should be made to perform the assessments outlined in the schedule of events. If the patient is unable to return to the study site, a follow-up phone call can

be made by the study site to collect any new safety information that occurred during the Safety Follow-up Period.

After the 30-Day Safety Follow-Up Visit (see below), patients who have not started treatment with a new anticancer therapy will be assessed for drug-related SAEs only.

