3.3.5. Survival Follow-Up

Once a patient discontinues study treatment, regardless of the reason, Survival Follow-Up will begin, unless the patient withdraws consent or the study is terminated early by the Sponsor. During this period, the patient or family should be contacted for Survival Follow-Up every 12 weeks (\pm 2 weeks) until survival events (deaths) have been reported for 75% of enrolled patients, patient withdraws consent or the study is terminated early by the Sponsor. In addition, all subsequent anticancer treatments will be recorded.

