Pregnancy test	Serum β human chorionic gonadotrophin (human chorionic stimulating hormone) test required for WOCBP
Ophthalmological examination	See Section 6.1
PK blood sampling	See Section 7 .

Assessment	Details
Pharmacodynamic biomarker blood sampling	See Section 10
Efficacy assessments	See Section 8.
Concomitant medication/concomitant therapy	Including all medications / therapies administered from the time informed consent has been documented through 30 days after administration of the last dose of study drug or until the start of new anticancer therapy.
AE monitoring	All AEs will be collected from the time informed consent has been documented until Safety Follow-Up Visit is completed after the last dose of any study drug (safety follow-up) or until the start of new anticancer therapy, whichever is earlier. See Section 9.

Abbreviations: AE=adverse event; ALT=alanine aminotransferase; ANC=absolute neutrophil count; AST=aspartate aminotransferase; CrCl=calculated creatinine clearance; ICF=informed consent form; QT = QT interval; QTcF = Fridericia's Correction Formula; RR=intra-beat; WOCBP=women of childbearing potential

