9.2.5. Follow-up of Adverse Events

Any ongoing AEs should be followed until the earliest occurrence of one of the following:

- The AE has resolved or stabilized
- Completion of Safety Follow-Up Visit
- Start of new antitumor therapy
- Withdrawal of consent
- Death
- Other (eg, transfer to another hospital)

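### SAP 7.5 censors unresolved AESIs at the last known alive date, so non-serious events in off-treatment patients stay at risk after their resolution has stopped being recorded

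*SAP*

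**What the plan says.** - **Censoring rule.** SAP 7.5: if a clustered AESI is unresolved, "the resolution date will be censored to the last known date that the patient was alive". No cap is set at the end of AE follow-up.
- **Where it is used.** SAP 5.6.2.6 plans a Kaplan-Meier curve, with median and quartiles, for time to resolution of selected Grade 3 or higher AESIs. It gives hyperphosphatemia as the example.
- **End of AE follow-up.** Protocol 9.2.5: "Any ongoing AEs should be followed until the earliest occurrence of one of the following". The list includes "Completion of Safety Follow-Up Visit" and the start of new antitumor therapy. Protocol Section 6 collects AEs "until Safety Follow-Up Visit is completed after the last dose of any study drug (safety follow-up) or until the start of new anticancer therapy", taking the earlier of the two.
- **Timing of that visit.** Protocol 3.3.3: "which must be performed 30 days (+7 days) following the last dose of study drug". After it, under Protocol 3.3, patients not yet on new therapy "will be assessed for drug-related serious adverse events (SAEs) only".
- **Survival follow-up.** Protocol 3.3.5: after treatment ends, "the patient or family should be contacted for Survival Follow-Up every 12 weeks", with a window of 2 weeks either side.
- **Time to onset, for comparison.** SAP 7.4: "time-to-onset will be censored at last dosing date +30 days if patients are off treatment" and have been followed for at least 30 days; otherwise the last known alive date is used.

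**The concern.** Censoring is meant to mark the last moment at which the event could have been seen. For a non-serious AESI in a patient who has stopped treatment, that moment is the Safety Follow-Up Visit or the start of new therapy. The last known alive date is later, and it advances with each survival contact. Between the two dates the patient counts in the denominator but cannot contribute a resolution.

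This affects how reversible the AESIs appear in the study report. A curve that flattens because nobody was recording resolutions looks the same as one that flattens because the events persist.

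**Working it through.** The documents give no resolution-time figure, so there is none to reproduce. The check has three parts.

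**1. Unobservable time, from the protocol windows.** Count both visits from last dose. The safety visit falls at day 30 to 37 and the first survival contact at 84 ± 14 days.
- Shortest gap: 84 − 14 − 37 = 33 days.
- Longest gap: 84 + 14 − 30 = 68 days.
- Each later contact adds about 84 days.

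**2. Mechanism, by hand.** The Kaplan-Meier estimate is S(t) = Π(1 − dᵢ/nᵢ), with dᵢ resolutions among nᵢ at risk. Take ten invented patients. Six resolve on days 5, 8, 12, 20, 40 and 60. Four are unresolved when AE follow-up ends on days 25, 30, 30 and 37, and all four are last known alive on day 200. Both rules give S = 0.6 after day 20.
- Censoring at end of AE follow-up: day 40, 0.6 × (1 − 1/2) = 0.3; day 60, 0.3 × (1 − 1/1) = 0.
- SAP rule: day 40, 0.6 × (1 − 1/6) = 0.5; day 60, 0.5 × (1 − 1/5) = 0.4.

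The median is 40 days under both rules. Estimated resolution by day 60 is 100% under the first and 60% under the SAP rule. The late part of the curve moves and the early part does not.

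**3. Size, by simulation (100,000 patients per scenario).** All of these inputs are assumptions:
- exponential resolution with median m of 14, 30 or 60 days;
- exponential treatment duration with mean 60, 120 or 240 days;
- onset uniform over treatment;
- AE observation ending 30 days after last dose;
- 0%, 30% or 60% of AESIs followed as SAEs until the alive date;
- mean survival follow-up beyond day 30 of 84 days, with 252 days also run for 0% SAEs.

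True resolution by day 84 is 1 − 0.5^(84/m). Ranges in the table run over treatment duration and, for 0% SAEs, over both survival lengths.

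| True median | True resolved by day 84 | SAP rule, 0% SAEs | SAP rule, 60% SAEs | SAP-rule median, 0% SAEs | SAP-rule median, 60% SAEs |
|---|---|---|---|---|---|
| 14 d | 0.984 | 0.898–0.949 | 0.952–0.971 | 14 d | 14 d |
| 30 d | 0.856 | 0.681–0.783 | 0.789–0.828 | 30 d | 30 d |
| 60 d | 0.621 | 0.444–0.545 | 0.554–0.593 | 69–260 d; not reached in one scenario | 63–68 d |

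- Censoring at the end of observation recovers the truth throughout: 0.984–0.986, 0.855–0.859 and 0.618–0.623 at day 84.
- At day 28 the two rules agree, because every simulated patient is observed for at least 30 days after onset.
- The unobservable share of SAP-rule person-time is 17–77% with no SAEs and 8–24% with 60% SAEs.

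A second set of assumptions agrees. Here AE follow-up ends 30 to 180 days after onset, survival follow-up runs a mean of 200 days longer, and no events are SAEs. Medians of 14 and 28 days are unchanged, with day-90 resolution of 0.966 against 0.988 and 0.841 against 0.892. A true median of 60 days is estimated at about 67, and one of 90 days at about 115.

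**The case against.** A reader might infer that no AESI resolution can be recorded after the safety visit, and that reported medians, for hyperphosphatemia in particular, will be inflated. The documents do not support that.
- Protocol 9.4.2 follows every SAE until it resolves, stabilizes or returns to baseline. Table 7 has Grade 3 and 4 ocular events reported as SAEs, and Grade 4 monitored until resolution or stabilization. The planned display covers only Grade 3 or higher AESIs, where SAEs are likelier.
- Protocol 9.3.2 repeats clinically significant laboratory tests, as clinically indicated, until baseline or stabilization. This helps only in part: Table 1 schedules no chemistry in survival follow-up, and 9.2.5 still ends follow-up of the AE.
- Nothing in the documents points to resolution medians of 60 days or more. At about 30 days or less the median does not change.
- Patients still on treatment at cut-off have an alive date close to their last AE assessment. Under SAP 4.3 the final analysis can come 6 months after the last patient's first dose, so years of excess follow-up cannot be presumed.

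A reader might also infer that SAP 7.4 and 7.5 contradict each other. They do not. The 7.4 cap matches the treatment-emergent window in SAP 7.2, 7.4 itself falls back on the alive date, and an on-treatment event may legitimately resolve later than last dose + 30 days. Different rules for onset and resolution are acceptable; what matters is whether each date marks the end of observation.

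All of this limits scope and size. It does not answer the mismatch for non-serious AESIs, and Grade 3 is not the same as serious.

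**Conclusion.** The rule is wrong as written, and the point is minor. The mismatch and its direction follow from the two documents: time at risk without observation can only lower the estimated probability of resolution. It applies to non-serious AESIs still unresolved when an off-treatment patient reaches the safety visit or starts new therapy.

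The size rests on the assumptions above. With no SAE follow-up, the day-84 shortfall is about 0.04 to 0.18 (0.984 − 0.949 and 0.621 − 0.444 are the extremes). With 60% SAEs it is about 0.01 to 0.07. Medians move upward only when true resolution is slow, at about 60 days or more, and the shift is large only when few events are SAEs. This is a descriptive secondary safety display; ORR, CR rate and error rates are unaffected.

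**What to change.** Replace the censoring sentence in SAP 7.5 with two rules:
- for unresolved non-serious clusters, censor at the earliest of the last AE assessment or Safety Follow-Up Visit, start of new anticancer therapy, death, or data cut-off;
- for events with documented extended follow-up (SAEs), censor at the last date on which that event was assessed.

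The second rule is needed. Censoring every unresolved event at the safety visit while still counting later SAE resolutions would bias the curve slightly upward. With 60% SAEs under the second set of assumptions, day-90 resolution is 0.658 against a true 0.646 (median 60 days) and 0.512 against 0.500 (median 90 days).

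The cost is a short SAP edit with no new procedures. The sponsor should confirm that a last-assessed date is held for each SAE, since the documents do not show that it is.
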